# 17. QUALITY OF LIFE ANALYSIS

Not Applicable

#### 18. SAFETY OUTCOMES

All outputs for safety outcomes will be based on the Safety Analysis Population.

There will be no statistical comparisons between the treatment groups for safety data, unless otherwise specified with the relevant section.

#### 18.1. ADVERSE EVENTS

Adverse Events (AEs) will be coded using Medical Dictionary for Regulatory Activities (MedDRA) central coding dictionary, Version 23.1.

Treatment emergent adverse events (TEAEs) are defined as AEs that started or worsened in severity on or after the first dose of study medication (Combination therapy).

See Appendix 2 for handling of partial dates for AEs. In the case where it is not possible to define an AE as treatment emergent or not, the AE will be classified by the worst case; i.e. treatment emergent.

An overall summary of number of patients within each of the categories described in the sub-section below, will be provided as specified in the templates. Listings will include TEAEs and Non-TEAEs.

#### **18.1.1.** ALL TEAES

Incidence of TEAEs will be presented by System Organ Class (SOC) and Preferred Term (PT) and broken down further by maximum severity and relationship to study medication.

#### 18.1.1.1. Severity

Severity is classed as mild/ moderate/ severe (increasing severity). TEAEs starting after the first dose of study medication with a missing severity will be classified as severe. If a patient reports a TEAE more than once within that SOC/ PT, the AE with the worst-case severity will be used in the corresponding severity summaries.

#### 18.1.1.2. Adverse Drug Reaction

An adverse drug reaction (ADR) is any untoward and unintended response to a study treatment related to any dose administered. The definition implies a reasonable possibility of a causal relationship between the event and the study

Document: \\ieedc-vnasc01\BIOSdata\Menarini\NebZof\KZA41200\Biostatistics\Documentation\SAP

Author: [name] Version Number: Final V1.0

Version Date: [14Dec2021]

Template No.: CS\_TP\_BS016 Revision 6 Reference: CS\_WI\_BS005

Effective Date: 02Dec2019

Page 29 of 37

treatment. In eCRF, if related, as indicated by the Investigator, is classed as "Certain Related", "Probable Related", "Possible Related", "Un-assessable", and if unrelated then classed as "Unlikely related", "Not related". TEAEs with a missing relationship to study medication will be regarded as "Probable Related" to study medication. If a patient reports the same AE more than once within that SOC/PT, the AE with the worst-case relationship to study medication will be used in the corresponding relationship summaries.

#### 18.1.2. TEAES LEADING TO DISCONTINUATION OF STUDY MEDICATION

Treatment-emergent Adverse Events leading to discontinuation of study medication are those events where for 'Reason treatment not completed' recorded as 'Adverse event'.

For TEAEs leading to discontinuation of study medication, summaries of incidence rates (frequencies and percentages) by SOC and PT will be prepared.

#### 18.1.3. SERIOUS ADVERSE EVENTS

Serious adverse events (SAEs) are those events recorded as "Serious" on the Adverse Events page of the (e)CRF. A summary of serious TEAEs by SOC and PT will be prepared.

#### 18.1.4. ADVERSE EVENTS LEADING TO DEATH

TEAEs leading to Death are those events which are recorded as "Fatal" on the Adverse Events page of the (e)CRF. A summary of TEAEs leading to death by SOC and PT will be prepared.

#### **18.2. DEATHS**

If any patients die during the study the information will be presented in a summary table and a data listing.

#### 18.3. LABORATORY EVALUATIONS

Results from the central laboratory will be included in the reporting of this study for Hematology, Blood Chemistry and Pregnancy test. A list of laboratory assessments to be included in the outputs is included in protocol Section 10.2.3. Laboratory evaluations will be summarized for Combination therapy by SAF population. Presentations will use SI Units.

The following summaries will be provided for laboratory data:

Document: \\ieedc-vnasc01\BIOSdata\Menarini\NebZof\KZA41200\Biostatistics\Documentation\SAP

Author: [name] Version Number: Final V1.0

Version Date: [14Dec2021]

Template No.: CS\_TP\_BS016 Revision 6 Reference: CS\_WI\_BS005

Page 30 of 37

- A descriptive summary of lab parameters by visit.
- The Shift from screening (visit 1)according to the lab result summary will be provided for laboratory data
- A by-patient listing of all laboratory data and pregnancy test data will be presented.

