#### 7. STUDY DESIGN

This is a phase IV, open-label, multicenter, multinational, interventional study to assess the effectiveness and safety of the extemporaneous combination of NEB and ZOF in grade 1 to 2 hypertensive patients versus each monotherapy (NEB or ZOF).

The study will be conducted in approximately 15 sites in the European Union countries. The total study duration is 12 weeks including a run-in period of 4 weeks and an assessment period of 8 weeks.

At Visit 1, after providing informed consent, the eligible grade 1-2 hypertensive patients (with blood pressure [BP] ranging from ≥140/90 mmHg to ≤179/109 mmHg), who were on treatment since at least 1 month, with any ACE-i or BB including ZOF 30 mg and NEB 5 mg will be screened for the eligibility criteria including BP. On the same day, the eligible patients will enter the run-in period of 4 weeks (Week -4 to Week 0). Efforts will be made to achieve 1:1 ratio in the enrolment of patients receiving any ACE-i or BB. The eligibility for grade 1-2 hypertension will be based upon the European Society of Cardiology/European Society of Hypertension (ESC/ESH) guidelines 2018, and the BP criteria is defined as mean sitting SBP ≥140 mmHg and ≤179 mmHg and/or mean sitting DBP ≥90 mmHg and ≤109 mmHg.

During the run-in period of 4 weeks (Week -4 to Week 0):

 Patients on ZOF 30 mg or NEB 5 mg will continue the same therapy. Patients on any other ACE-i will be assigned to monotherapy with ZOF 30 mg and the patients on any other BB will be assigned to monotherapy with NEB 5 mg, respectively.

Patients with controlled BP (sitting SBP/DBP ≤130/80 mmHg), at Week 0 (Visit 2), patients with uncontrolled BP (sitting SBP/DBP >130/80 mmHg) whose adherence to the treatment is not included from 80% to 120% or patients who cannot tolerate one of the monotherapies will not proceed further into the study.

Identification Number: FORM-000050125

Previous Doc Number:
CTWI10A

Version Number: 1.0, CURRENT

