### 18.4. ECG EVALUATIONS

Results from the central ECG (Electrocardiogram) Reading Centre will be included in the reporting of this study. The following ECG parameters will be reported for this study:

- PQ Interval (PR) (msec)
- QRS Interval (msec)
- QT Interval (msec)
- QTc Interval (msec)
- HR (bpm)
- Overall assessment of ECG (Investigator's judgment):
  - o Normal
  - Abnormal, Not Clinically Significant (ANCS)
  - o Abnormal, Clinically Significant (ACS)

ECG parameters will be summarized descriptively using the safety population for the Combination therapy. All ECG data will be listed.

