### 18.5. VITAL SIGNS

The following Vital Signs measurements will be reported for this study:

- Sitting [/ Standing/ Supine] Systolic Blood Pressure (mmHg)
- Sitting [/Standing/ Supine] Diastolic Blood Pressure (mmHg)
- Pulse Rate (bpm)
- Respiratory Rate (breaths/min)
- Temperature (C)

The following summaries for both Monotherapy and Combination therapy, will be provided for vital signs data:

Actual and change from baseline by visit.

Document: \\ieedc-vnasc01\BIOSdata\Menarini\NebZof\KZA41200\Biostatistics\Documentation\SAP

Author: [name] Version Number: Final V1.0

Version Date: [14Dec2021]

Template No.: CS\_TP\_BS016 Revision 6 Reference: CS\_WI\_BS005

Effective Date: 02Dec2019

Page 31 of 37

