#### 18.6. PHYSICAL EXAMINATION

The following summaries will be provided for physical examination data for combination therapy by visit on SAF:

- Summary of Physical examination
- Shift from baseline according to the physical examination findings.

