#### PRESENTATION OF TREATMENT GROUPS

For outputs, treatment groups will be represented as follows and in the given order:

Therapy	Treatment Group	For Tables and Graphs	For Listings (include if different to tables)
Monotherapy	NEB 5mg	NEB 5mg	NEB 5mg
Monotherapy	ZOF 30mg	ZOF 30mg	ZOF 30mg
Combination therapy	NEB+ZOF	NEB+ZOF	NEB+ZOF

Document: \\ieedc-vnasc01\BIOSdata\Menarini\NebZof\KZA41200\Biostatistics\Documentation\SAP

Author: [name] Version Number: Final V1.0

Version Date: [14Dec2021]

Template No.: CS\_TP\_BS016 Revision 6 Reference: CS\_WI\_BS005

Effective Date: 02Dec2019

Page 34 of 37

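### The SAP text summarises combination-period safety in one NEB+ZOF group, so an excess confined to patients newly given one of the drugs is shown at about half its size

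*SAP*

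**What the plan says.** The table of treatment groups in SAP Appendix 1 says that "treatment groups will be represented as follows and in the given order" and then lists NEB 5 mg and ZOF 30 mg as monotherapies and one combination group, NEB+ZOF.

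The safety sections of the SAP read as follows.

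- **18.3 Laboratory:** "Laboratory evaluations will be summarized for Combination therapy by SAF population".
- **18.4 ECG:** "ECG parameters will be summarized descriptively using the safety population for the Combination therapy".
- **18.6 Physical examination:** summaries of "physical examination data for combination therapy by visit on SAF".
- **18.5 Vital signs:** "The following summaries for both Monotherapy and Combination therapy, will be provided for vital signs data". No division of the combination group is stated.
- **18.1 and 18.1.1 Adverse events:** the treatment-emergent period starts with the first combination dose. Incidence is given by organ class and preferred term, "broken down further by maximum severity and relationship to study medication". No treatment columns are named.

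SAP 7.5 does define run-in therapy (ZOF or NEB) as a subgroup, but ties the subgroups to the exploratory analysis sections on the ITT and PP populations. Those sections (16.3) concern blood pressure. No safety section uses this subgroup.

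Under Protocol Section 7, patients on an ACE inhibitor have ZOF in the run-in and patients on a beta blocker have NEB. Those still uncontrolled at Visit 2 then receive both. The protocol aims for a 1:1 ratio, with a cap of 110 per run-in drug.

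**The concern.** The NEB+ZOF group holds two different new exposures. Patients from the ZOF run-in start a beta blocker at Visit 2, and patients from the NEB run-in start an ACE inhibitor. Each half has already been selected for tolerating its continuing drug, because "patients who cannot tolerate one of the monotherapies will not proceed further into the study". The inclusion criteria also require at least one month of monotherapy in that class before screening. Heart rate below 60 bpm is an exclusion at screening, when the patients bound for NEB are already on a beta blocker and the others are not.

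If a reaction arises mainly on first exposure, a single column averages patients at risk of it with patients who have already come through it. A fall in pulse or a longer PR interval after adding NEB, or a potassium or creatinine change after adding ZOF, would look smaller than it is in the patients who have just started that drug. Tolerability is a secondary objective, and the SAP text describes no other safety summary that shows it by the drug newly added.

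**Working it through.** **1. The plan's own figures.** The documents state no safety event rate, so there is none to reproduce. The relevant planned figures are the total of 216 and the cap of 110 (Protocol 14.2 and 7). The 216 reproduces from a net DBP effect of 4 − 2 = 2 mmHg, SD 10, 90% power and a one-sided 5% level: n = [(1.645 + 1.282) × 10 / 2]² = 214.2, rounded up to 215; with the t distribution, 216. It serves here only as a denominator.

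**2. Share of patients newly given a drug, w.**

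- Both caps reached: w = 110/220 = 0.50.
- 216 patients, one group at its cap: 110/216 = 0.509 and 106/216 = 0.491.
- Protocol Section 7 starts corrective action when entry deviates by more than 5%. Read as 5 percentage points (an assumption), w lies between 0.45 and 0.55.

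**3. What the pooled column shows.** Let p_new be the risk in patients newly given the drug and p_cont the risk in those continuing it.

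- Pooled rate = w·p_new + (1 − w)·p_cont.
- Hence (pooled − p_cont) / (p_new − p_cont) = w.

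The excess due to new exposure is therefore shown at w of its size: about one half, 45 to 55% on the range above. The same algebra holds for a mean change. If new users change by x bpm and continuing users by 0, the pooled mean is w·x, or x/2 at w = 0.5.

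**4. Total incidence.** With w = 0.5 and an assumed p_new of 10%:

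| p_cont | Pooled rate | Pooled / p_new |
|---|---|---|
| 0% | 5.0% | 0.50 |
| 2% | 6.0% | 0.60 |
| 5% | 7.5% | 0.75 |
| 10% | 10.0% | 1.00 |

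Only the first row is a halving of the rate itself.

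**5. Illustration (assumed counts).** Eleven events, all in newly exposed patients: 11/108 = 10.2% (exact 95% CI 5.2 to 17.5%) in the split column and 11/216 = 5.1% (2.6 to 8.9%) in the pooled one.

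**6. What a split could support.** With n = 108 per column, two-sided 5% and mean rate p̄, power = Φ{[|p₁ − p₂| − 1.96·√(2p̄(1 − p̄)/n)] / √[(p₁(1 − p₁) + p₂(1 − p₂))/n]}.

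- 10% against 2%: (0.08 − 0.0633)/0.0319 = 0.52, power about 70%.
- 10% against 5%: (0.05 − 0.0703)/0.0357 = −0.57, power about 29%.

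**7. Reference visit.** SAP 6.2 takes Visit 1 as the laboratory baseline because no laboratory test is done at Visit 2. For patients who changed to ZOF or NEB at Visit 1, the change to Visit 3 therefore combines a within-class switch with the add-on. ECG and vital signs are recorded at Visit 2 and do not have this problem.

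**The case against.** The strongest reply is that the pooled column answers the stated question. The objective for the assessment period is the safety and tolerability of the combination. Everyone in the column takes both drugs, and no objective asks about adding each drug separately. This stands: pooling is a valid summary and not an error.

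A reader might go further than the documents allow in three ways.

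- **That every harm of a new drug is halved.** Step 4 shows that only the excess over continuing patients is. Without rates in the documents, the pooled-to-new ratio could lie anywhere from 0.5 to 1.0 when continuing patients have the lower or equal risk. Harms of taking both drugs together can occur in both halves and need not be diluted.
- **That every safety table is pooled.** SAP 8 and 18.1 leave layouts to templates that are not in the published text. The adverse event sections name no columns, and vital signs are also shown for monotherapy.
- **That a zero-event upper bound would look too tight.** The safety sections plan summaries and listings, not confidence bounds for event rates, and a bound on the pooled group would be correct for that group.

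The planned listings of adverse events, laboratory and ECG data, with drug accountability by phase, would also let someone rebuild the split. No information is lost, but the rebuilt summary would be post hoc.

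Finally, the two halves are not randomised. They differ by prior drug class, and power to compare them is limited. That argues for descriptive columns, not against having them.

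**Conclusion.** On the written SAP, no safety summary separates patients newly given NEB from patients newly given ZOF. An excess rate or mean change confined to newly exposed patients would be shown at about half its size, roughly 45 to 55%. This rests on the planned 1:1 entry and, for the range, on reading the 5% trigger as percentage points. How far any total rate is understated cannot be settled from the documents. It depends on how often continuing patients have the same event.

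A split by drug added is a worthwhile, low-cost improvement to how tolerability is reported. It would prespecify a summary by new exposure that the data already allow.

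**What to change.** - Keep the NEB+ZOF total. Beside it add two descriptive sub-columns, run-in NEB (ZOF added) and run-in ZOF (NEB added), for treatment-emergent events and adverse drug reactions (SAP 18.1), laboratory (18.3), ECG (18.4) and vital signs (18.5).
- Change the Appendix 1 treatment-group table and the table templates to match.
- State in the SAP that the sub-columns are non-randomised and not for formal comparison.
- State that laboratory changes run from Visit 1, so that in patients who switched drug at Visit 1 they combine the within-class switch with the add-on. The column split does not remove this.

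This takes SAP and table-shell wording and no new data. The costs are wider tables, about 108 patients in each sub-column, and a risk that readers compare the two groups informally.

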### 18.4. ECG EVALUATIONS

Results from the central ECG (Electrocardiogram) Reading Centre will be included in the reporting of this study. The following ECG parameters will be reported for this study:

- PQ Interval (PR) (msec)
- QRS Interval (msec)
- QT Interval (msec)
- QTc Interval (msec)
- HR (bpm)
- Overall assessment of ECG (Investigator's judgment):
  - o Normal
  - Abnormal, Not Clinically Significant (ANCS)
  - o Abnormal, Clinically Significant (ACS)

ECG parameters will be summarized descriptively using the safety population for the Combination therapy. All ECG data will be listed.

### 18.5. VITAL SIGNS

The following Vital Signs measurements will be reported for this study:

- Sitting [/ Standing/ Supine] Systolic Blood Pressure (mmHg)
- Sitting [/Standing/ Supine] Diastolic Blood Pressure (mmHg)
- Pulse Rate (bpm)
- Respiratory Rate (breaths/min)
- Temperature (C)

The following summaries for both Monotherapy and Combination therapy, will be provided for vital signs data:

Actual and change from baseline by visit.

Document: \\ieedc-vnasc01\BIOSdata\Menarini\NebZof\KZA41200\Biostatistics\Documentation\SAP

Author: [name] Version Number: Final V1.0

Version Date: [14Dec2021]

Template No.: CS\_TP\_BS016 Revision 6 Reference: CS\_WI\_BS005

Effective Date: 02Dec2019

Page 31 of 37

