### 6. GENERAL CONSIDERATIONS

### **6.1.** REFERENCE START DATE AND STUDY DAY

Study Day will be calculated from the reference start date and will be used to show start/stop day of assessments and events. Reference start date is defined as the day of the first dose of study drug (combination therapy) (Visit 2), (Day 1 is the day of the first dose of study drug ) and will appear in every listing where an assessment date or event date appears.

- If the date of the event is on or after the reference date, then:
- Study Day = (date of event reference date) + 1. If the date of the event is prior to the reference date, then: Study Day = (date of event – reference date).

In the situation where the event date is partial or missing, Study Day, and any corresponding durations will appear partial or missing in the listings.

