#### **6.2.** BASELINE

Unless otherwise specified, baseline is defined as the last non-missing measurement taken same day or prior to reference start date (including unscheduled assessments) before first dose of study medication (combination therapy). Adverse Events (AEs) and medications commencing on the reference start date/time will be considered post-baseline, unless the start time of the AE is known to be prior to the first dosing of the study drug. Since there is no Lab assessment in Visit 2, Lab values collected at Visit 1 will be considered baseline for Lab data.

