#### **6.6.** COMMON CALCULATIONS

For quantitative measurements, change from baseline will be calculated as:

• Test Value at Visit X – Baseline Value

And for change from Visit 1 will be calculated as:

• Test Value at Visit X – Visit 1 Value

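### SAP 18.5 measures the monotherapy change in vital signs from the end of the run-in, so at Visit 2 it is normally zero by construction

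*SAP*

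**What the plan says.** SAP 18.5 introduces its tables with "The following summaries for both Monotherapy and Combination therapy, will be provided for vital signs data" and asks for "Actual and change from baseline by visit". The parameters are blood pressure, pulse, respiratory rate and temperature. SAP Appendix 1 lists the treatment groups as NEB, ZOF and NEB+ZOF.

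Under SAP 6.2, unless a section says otherwise, "baseline is defined as the last non-missing measurement taken same day or prior to reference start date", and the value must fall "before first dose of study medication (combination therapy"). SAP 6.1 adds: "Reference start date is defined as the day of the first dose of study drug (combination therapy) (Visit 2"). The one exception in SAP 6.2 concerns laboratory data. SAP 18.5 names no other baseline.

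SAP 6.6 defines change from baseline as the visit value minus the baseline value. It then gives a second formula, introduced by "And for change from Visit 1 will be calculated as", which subtracts the Visit 1 value. SAP 18.5 does not call on that second formula.

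SAP 18 bases all safety outputs on the Safety population, which under SAP 5.3 requires at least one dose of the combination.

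**The concern.** Monotherapy runs from Visit 1 to Visit 2 and the combination from Visit 2 to Visit 3. A baseline at Visit 2 is right for the combination. For monotherapy it is the end of the period being described, so the change cannot show what happened during it.

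The safety and tolerability of each monotherapy is part of a stated secondary objective (SAP 2.2; Protocol 6), and vital signs are one of its measures. SAP 18.5 is also the only part of SAP 18 that plans a summary for monotherapy by name. Treatment-emergent events are counted from the first combination dose (SAP 18.1), and laboratory, ECG and physical examination summaries are for the combination (SAP 18.3, 18.4, 18.6). At stake is whether the one planned change summary for the monotherapies carries any information, for example on pulse under NEB.

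**Working it through.** The plan gives no figure to reproduce here. The check applies its own definitions.

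**Inputs**
- Vital signs and blood pressure are taken at Visits 1, 2 and 3 (Protocol 4.1). Call the values V1, V2 and V3.
- On visit days the drug is taken after the assessments (Protocol 7), so V2 precedes the first combination dose.
- Baseline B is the last value before that dose (SAP 6.1 and 6.2), so B = V2 unless a later unscheduled pre-dose reading exists.
- Change = visit value − B (SAP 6.6).

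**Result at each visit**
- Visit 1: V1 − V2 = −(V2 − V1), the run-in change with its sign reversed.
- Visit 2: V2 − V2 = 0.
- Visit 3: V3 − V2, the correct contrast for the combination.

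A run-in fall of 5 mmHg would therefore appear as 0 at Visit 2 and, if a Visit 1 change is printed, as +5 there.

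**Numerical confirmation.** The documents give no run-in effect, so a range was assumed. Each row simulates 216 patients with Visit 1 DBP of mean 95 and SD 6 mmHg, a run-in change with SD 7, and a combination change of mean −4 and SD 10.

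| Assumed run-in change | Simulated mean V2 − V1 | SAP 18.5 as written, Visit 1 | Visit 2 | Visit 3 |
|---|---|---|---|---|
| −8 | −8.56 | +8.56 | 0.00 | −3.49 |
| −5 | −5.36 | +5.36 | 0.00 | −3.66 |
| −2 | −1.96 | +1.96 | 0.00 | −3.13 |
| 0 | −0.21 | +0.21 | 0.00 | −3.38 |
| +3 | +3.53 | −3.53 | 0.00 | −3.89 |

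The Visit 2 entry does not depend on the run-in effect. The SAP 6.6 change from Visit 1, evaluated at Visit 2, gives the second column. The algebra is the same for every vital sign.

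**Is the run-in change reported elsewhere?** SAP 16.3.1 lists the Visit 1 to Visit 2 change in sitting SBP and DBP, grouped by patients already on ZOF or NEB versus patients switched to them. SAP 7.5 lists run-in drug as a subgroup, but SAP 16.3 applies those subgroups only to the proportion reaching the blood pressure goal. No section gives a run-in change for pulse, standing blood pressure, respiratory rate or temperature.

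**The case against.** The strongest reply is that little is lost.

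- **Actual values.** SAP 18.5 also prints actual values by visit. Where the same patients contribute at Visits 1 and 2, the mean change is the difference of two printed means. The safety endpoint in Protocol 6 refers to vital signs at Week 0 and Week 8, which actual values satisfy. This stands, but the spread of the within-patient change cannot be recovered from the two visit summaries.
- **Exploratory analysis.** Sitting SBP and DBP are covered by SAP 16.3.1. This stands, so it would be wrong to infer that the run-in effect is missing from the report altogether. That analysis does not separate NEB from ZOF, and it omits the other vital signs.
- **Loose wording.** SAP 16.3.2 uses the word baseline for Visit 1, SAP 6.2 allows other definitions, and SAP 6.6 has the needed formula. A programmer might therefore choose correctly. But SAP 16.3.2 names Visit 1 explicitly and SAP 18.5 does not, so the default rule governs.
- **Reversed sign.** A reader might infer that a wrong-signed row will certainly appear. SAP 8 leaves format to templates that are not in the documents. If the Visit 1 change is left blank, only the zero remains.
- **Zero for everyone.** This is also too strong, because SAP 6.2 admits unscheduled readings. A later pre-dose reading could make the Visit 2 change non-zero, though it would still not be the run-in change.
- **Patients who leave in the run-in.** They have no combination dose and hence no baseline, but the Safety population rule already excludes them. The baseline definition is not what removes them.
- **Laboratory data.** A reader might extend the point to "Laboratory evaluations will be summarized for Combination therapy by SAF population", since SAP 6.2 says "Lab values collected at Visit 1 will be considered baseline for Lab data". The documents do not support that extension. SAP 18.3 openly describes the shift as starting from screening, and no Visit 2 sample is scheduled. Retitling the table would change no result.

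**Conclusion.** The point holds for vital signs. Under the rule as written, the monotherapy change at Visit 2 is 0 for each patient whose Visit 2 reading is the baseline, whatever happened in the run-in. Any change shown at Visit 1 would have the opposite sign to the run-in change, on condition that the table prints it. This is a stated rule with an uninformative result, not a missing detail.

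The practical loss is the within-patient run-in change, by drug, in pulse, standing blood pressure, respiratory rate and temperature. For sitting SBP and DBP the loss is smaller: the change is listed as exploratory, without a NEB versus ZOF split. The tables concerned are descriptive. The primary and secondary efficacy results are unaffected, since they rest on Visits 2 and 3.

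The conclusion assumes that SAP 18.5 follows the SAP 6.2 default, and that the unseen table templates do not override it.

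**What to change.** In SAP 18.5, state that for the NEB and ZOF columns the change is Visit 2 minus Visit 1, using the change from Visit 1 already defined in SAP 6.6. For the combination column it is Visit 3 minus Visit 2.

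Add an exception to the population rule in SAP 18, so that the monotherapy vital-signs table uses all enrolled patients who took the run-in drug and have a Visit 2 value. SAP 14 and 15 already use the Enrolled population for monotherapy exposure and compliance, so this follows the plan's own practice. Identify the visits in this table by their nominal label, because a patient with no combination dose has no reference start date and so no study day.

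The cost is one derived variable and one table on a different population. The readings are already scheduled at all three visits, so no new data are needed.
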